8.6 Expedited Reporting

The Sponsor/designee will report all relevant information about Suspected Unexpected Serious Adverse Reactions (SUSARs) that are fatal or life-threatening as soon as possible to the Food and Drug Administration (FDA) and in any case no later than 7 days after knowledge by the Sponsor/designee of such a case. Relevant follow-up information will subsequently be communicated within an additional 8 days.

All other SUSARs will be reported to the FDA as soon as possible but within a maximum of 15 days of first knowledge by the Sponsor/designee.

The Sponsor/designee will also report any additional expedited safety reports required in accordance with the timelines outlined in country-specific legislation.

The Sponsor/designee will also inform all Investigators as required per local regulation.

The requirements above refer to the requirements relating to investigational therapeutic product.

8.7 Clinical Laboratory Evaluations

CBC with differential will be performed at screening, Days 1, 3, 5, 7, 8, 10, 12, and 14. If the patient remains hospitalized, will also be performed on Days 15 and 29. If the screening assessment was obtained within 24 hours of Day 1 dosing, it is not necessary to repeat the CBC prior to Day 1 dosing.

Metabolic panel/chemistry assessments will be performed at screening, Days 1 and 8 (within 24 hours prior to dosing) and as clinically indicated. If the patient remains hospitalized, will also be performed on Days 15 and 29. If the screening assessment was obtained within 24 hours of Day 1 dosing, it is not necessary to repeat the chemistries prior to Day 1 dosing. Lactate dehydrogenase test should be repeated daily if elevated above the upper limit of normal.

Hemoglobin A1c will only be obtained at screening if the patient does not have a value within 90 days prior to screening.

Urine dipstick is acceptable and microscopic analyses can be performed if clinically indicated. If $\geq 2+$ protein on urine dipstick, then a spot urine sample should be collected in order to calculate the urine protein to creatinine ratio or a 24-hour urine should be collected.

Clinical laboratory analytes are listed in [Appendix B](#).

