3 STUDY DESCRIPTION

3.1 Summary of Study Design

This is an interventional, multicenter, 2-arm, parallel-group, randomized, double-blind, placebo-controlled, dose-escalation, safety and efficacy study of F-652 treatment versus placebo in patients aged 18 years or older with a COVID-19 diagnosis confirmed by polymerase chain reaction (PCR). Eligible patients will have moderate to severe COVID-19 symptoms and will be hospitalized. Figure 1 provides an overview of the study design.

AE = adverse event; COVID-19 = coronavirus disease 2019; ECG = electrocardiogram; NIAID = National Institute of Allergy and Infectious Diseases; PCR = polymerase chain reaction; PD = pharmacodynamic(s); SAE = serious adverse event; SARS-CoV-2 = severe acute respiratory syndrome coronavirus 2; TEAE = treatment-emergent adverse event.

The study plans to include 4 cohorts (see [Table 1](#)), with enrolled patients being randomized 1:1 in a blinded manner on Day 1, following screening, to F-652 or placebo as follows:

- Cohort 1 (sentinel cohort): Four patients will receive either [REDACTED] or placebo. Two patients will receive F-652 and 2 patients will receive placebo. Upon completion of sentinel dosing (7 days after last patient last dose), the Data Monitoring Committee (DMC) will evaluate the safety and tolerability data of the sentinel patients and determine if it is acceptable to dose the remaining patients in this dosing group in Cohort 2.
- Cohort 2: Fourteen patients will receive either [REDACTED] or placebo. Seven patients will receive F-652 and 7 patients will receive placebo. Upon completion of Cohort 2, the DMC will convene and review all available safety data to determine if the study can proceed to the next dose level.

- Cohort 3 (sentinel cohort): Four patients will receive either [REDACTED] or placebo. Two patients will receive F-652 and 2 patients will receive [REDACTED]. Upon completion of sentinel dosing (7 days after last patient last dose), the DMC will evaluate the safety and tolerability data of the sentinel patients and determine if it is acceptable to dose the remaining patients in this dosing group in Cohort 4. [REDACTED]
- Cohort 4: Sixteen patients will receive either [REDACTED] or placebo. Eight patients will receive F-652 and 8 patients will receive placebo. [REDACTED]

Table 1. Dosing Strategy

Cohort	Number of Patients	Dosing
1 (sentinel)	4	[REDACTED]
2	14	[REDACTED]
3 (sentinel)	4	[REDACTED]
4	16	[REDACTED]

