4.3.2 Criteria for Study Termination

In the event that any of the following are encountered, the DMC will convene as soon as possible to determine if the study must stop enrollment:

- SAE considered related to study drug;
- \geq Grade 3 (CTCAE v5.0) reaction considered related to study drug;
- ≥ 2 patients are discontinued from treatment for safety reasons pertaining to study drug per DMC decision;

- ≥ 2 patients experience similar SAEs or Grade 3 (CTCAE v5.0) AEs related to study drug per DMC decision; and/or
- ≥ 2 patients experience worsening of cytokine release syndrome related to study drug per DMC decision.

The following will not be considered as criteria for study termination:

- Grade 3 to 4 fever if present at study entry;
- Grade 3 nausea if it resolves to \leq Grade 1 within 72 hours;
- Grade 3 fatigue, malaise, or insomnia if it resolves to \leq Grade 1 within 72 hours; and/or
- \leq Grade 4 isolated electrolyte abnormalities that resolve with or without intervention to \leq Grade 2 within 72 hours.

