8 SAFETY ASSESSMENTS

8.1 Safety Endpoints

The safety endpoints include the following:

- All cause TEAEs and SAEs;
- Change from screening (baseline) in clinical symptoms and abnormal vital signs, abnormal laboratory tests (e.g., complete blood count [CBC], serum chemistry, routine urinalysis, and coagulation function), and 12-lead electrocardiograms (ECGs); and
- Relationship of any observed AEs with F-652 treatment based on the Investigator's judgement.

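### As the text of Section 8.7 reads, a sentinel patient discharged before Day 15 may reach the DMC review with no scheduled chemistry panel after the second infusion

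*Combined protocol and SAP*

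**What the plan says.** Section 8.7 sets the chemistry schedule: "Metabolic panel/chemistry assessments will be performed at screening, Days 1 and 8 (within 24 hours prior to dosing) and as clinically indicated". It then adds a conditional part: "If the patient remains hospitalized, will also be performed on Days 15 and 29". One analyte has its own rule: "Lactate dehydrogenase test should be repeated daily if elevated above the upper limit of normal". Blood counts are listed more densely, and without a hospital condition up to Day 14: "CBC with differential will be performed at screening, Days 1, 3, 5, 7, 8, 10, 12, and 14".

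Section 3.1 puts the infusions on Days 1 and 8. It provides for discharge before Day 8: the patient then returns as an outpatient for the second infusion and is observed for about two hours.

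Cohorts 1 and 3 are sentinel cohorts of four patients, two of them on F-652. The DMC review comes seven days after the last sentinel patient's final infusion, and its purpose is to "evaluate the safety and tolerability data of the sentinel patients and determine if it is acceptable to dose the remaining patients". After Cohort 2, "the DMC will convene and review all available safety data to determine if the study can proceed to the next dose level"; no interval is stated for that review.

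Section 8.1 counts "serum chemistry, routine urinalysis, and coagulation function" among the laboratory safety endpoints. Appendix B lists the chemistry panel, which includes transaminases, bilirubin, creatinine, amylase and lipase. Section 6 refers to Appendix A for the schedule of procedures. The Appendix A grid and the text of Section 3.2.1 (criteria for DMC review) are not visible in the public document.

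**The concern.** The sentinel reviews decide whether the rest of a dose group may be treated, and they are timed from the last dose. They are meant to take in what follows both infusions. For a patient who has gone home, the last scheduled panel in 8.7 reflects one infusion only. With two F-652 patients per review, one missing profile is half of the active evidence on chemistry at that point.

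What could be missed is narrow but relevant: a liver, renal or pancreatic change after the second infusion that causes no symptoms and so prompts no test. The Cohort 2 review, which opens the next dose level, draws on whatever safety data exist. It has the same gap for any of its patients discharged before Day 15.

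**Working it through.** The plan gives no figure for this point, so the check is a count of scheduled panels against dosing and review days.

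**Inputs**
- Infusions: Days 1 and 8 (Section 3.1).
- Chemistry without a hospital condition: screening, Day 1 and Day 8, the last two drawn before dosing (8.7).
- Chemistry for inpatients only: Days 15 and 29 (8.7).
- Blood counts listed after the second infusion and before Day 15: Days 10, 12 and 14 (8.7).
- Cohort sizes: 4, 14, 4 and 16, with 2, 7, 2 and 8 patients on F-652 (3.1).

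**Steps**
1. Cohort total: 4 + 14 + 4 + 16 = 38, which agrees with Section 9.2.5.
2. Earliest sentinel review: Day 8 + 7 = Day 15 of the last sentinel patient.
3. Scheduled panels after the Day 8 infusion for a patient discharged before Day 15: none of screening, Day 1 or Day 8 (pre-dose) falls after it, and Days 15 and 29 do not apply. The count is 0.
4. For a patient still in hospital, the count by the earliest review is 1 (Day 15). For the last sentinel patient that panel falls on the review day itself.
5. F-652 patients behind each sentinel review: 2. So 0, 1 or 2 of them may lack a scheduled panel after the second infusion.
6. F-652 patients treated before the dose-level decision: 2 + 7 = 9. The same rule applies to each.
7. A panel added on Day 14 would come 14 − 8 = 6 days after the second infusion and 15 − 14 = 1 day before the earliest sentinel review. The count in step 3 would become 1.
8. Sentinel patients in all, both arms: 4 + 4 = 8.

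**The case against.** The strongest objection is that the deciding sources cannot be seen. Whether a discharged patient has blood drawn for chemistry after Day 8 is an entry in the Appendix A grid, and Section 3.2.1 may set the minimum data for a DMC review. Their absence from the public text is not a fault of the plan. This stands, and it limits the point to the body text. It does not remove it: 8.7 is not silent on discharged patients, since it expressly ties the later panels to staying in hospital. If Appendix A says otherwise, 8.7 needs to match it.

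Second, Section 8 seems to be written with inpatients in mind. Section 8.9 asks for at least four hours of vital signs after each infusion, although an outpatient is observed for about two. So the Day 14 blood count may in practice be done only in inpatients, even though 8.7 attaches no such condition. This also stands: the contrast between blood counts and chemistry is a contrast in wording, and the cost of the fix must allow for it.

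Third, other routes can yield chemistry: clinically indicated tests, daily LDH if elevated, and the rule in Section 8.2 that clinically significant abnormal values are followed until they settle. The Day 8 pre-dose panel shows the effect of one infusion. Adverse events are collected to Day 60, and nothing visible obliges the DMC to proceed on thin data. All of this narrows the gap. What remains is a change that nothing prompts anyone to measure.

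A reader might also infer that the rule in 4.3.2 on "isolated electrolyte abnormalities that resolve with or without intervention to" Grade 2 or below within 72 hours cannot work without more panels. The documents do not support that. The rule concerns an abnormality already detected, and the Section 8.2 follow-up then applies. A single Day 14 panel could not show resolution within 72 hours in any case.

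**Conclusion.** The point holds for the body text of 8.7. A sentinel patient discharged before Day 15 has no scheduled chemistry panel after the second infusion and may reach the DMC review without one. It rests on two conditions: that Appendix A and Section 3.2.1 do not add an outpatient panel or require one for the review, and that some sentinel patients do go home before Day 15, which the protocol foresees.

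The size is a count, zero scheduled panels for such a patient with two F-652 patients per review, and not a probability. A reader might infer that most sentinel reviews would be affected. The documents give neither a discharge rate nor the share of patients who would have clinically indicated chemistry. Let *d* be the share discharged before Day 15 and *c* the share of these tested anyway, with the two patients taken as independent. The chance that at least one of two lacks chemistry is 1 − (1 − *d*(1 − *c*))². With *d* = 0.2 and *c* = 0.9 this is 1 − 0.98² = 4%; with *d* = 0.8 and *c* = 0 it is 1 − 0.2² = 96%. Both pairs are assumptions, and a range that wide says nothing about this trial.

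It would also go too far to say that the DMC will lack chemistry data, or that safety monitoring stops after Day 8. This is a cheap improvement to the schedule, not a demonstrated error.

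**What to change.** First check Appendix A and Section 3.2.1. If they already provide an outpatient panel before the review, one line in 8.7 to match is enough.

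If they do not, add the Appendix B chemistry panel to the Day 14 draw in both 8.7 and Appendix A, for all patients regardless of discharge. The minimum version covers only the eight patients in Cohorts 1 and 3. Because Day 14 is one day before the earliest sentinel review, say that the result is to be in hand for that review.

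The cost is one extra tube per patient: at most 38, or 8 in the minimum version. If Day 14 draws are in practice done only in inpatients, the cost becomes one outpatient visit per discharged patient, at most 8 visits in the minimum version. One panel six days after the infusion can still miss a change that has come and gone by then.

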8.8 Viral Testing

A SARS-CoV-2 test will be performed on Day 1 (pre-dose), Day 4 (± 1 day), Day 8 (pre-dose), Day 11 (± 1 day), Day 14 (± 1 day), and prior to discharge on Days 15 and 29. Patients will have a naso-pharyngeal swab collected at screening and analyzed using PCR. If possible, a central laboratory should be used to confirm local laboratory results.

8.9 Vital Signs

Vital signs will include systolic and diastolic blood pressure, respiration, pulse, and oral temperature, and should be taken prior to study drug infusion, every 15 minutes during the infusion, at the end of the infusion, and hourly post-infusion, for a minimum of 4 hours after each infusion within a window of ± 5 minutes. Vital signs should be collected on a daily basis and may be collected more frequently if clinically indicated. Patients should be in a sitting position for at least 5 minutes prior to collection.

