Treatment will begin on Day 1 following randomization. Patients assigned to active drug will receive a total of 2 doses of F-652 (1 IV infusion on Day 1 and 1 IV infusion on Day 8). Patients assigned to placebo will receive identical IV infusions of placebo vehicle on Days 1 and 8. If the patient is discharged from the site prior to Day 8, they will return for an outpatient visit to receive the second IV infusion and remain at the site for an approximate 2-hour observation period. All patients will receive available supportive and antiviral therapies as standard of care. Efficacy will be assessed on Days 15 and 29. Patients will be followed for safety until Day 60.

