5.5.3 Study Drug Administration

F-652 will be administered, based on the patient's most recent weight, at a dose [REDACTED] IV on Days 1 and 8. Placebo vehicle will be identical in appearance to the study drug and will be administered IV on Days 1 and 8. If the patient is discharged from the site prior to Day 8, they will return for an outpatient visit to receive the second IV infusion and remain at the site for an approximate 2-hour observation period. [REDACTED]
[REDACTED]
[REDACTED]

The definitions and management of infusion related reactions are described in [Appendix C](#).

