6 STUDY PROCEDURES

Study procedures will follow the Schedule of Procedures ([Appendix A](#)).

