9.2.5 Sample Size Determination

The study plans to randomize 38 patients, with 4 patients in Cohort 1 (sentinel cohort), 14 patients in Cohort 2, 4 patients in Cohort 3 (sentinel cohort), and 16 patients in Cohort 4. The sample size is based on the purpose of the study and experience with similar proof-of-concept studies, and not based on statistical power calculation.

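### Outpatients stay about 2 hours after the Day 8 infusion, but section 8.9 asks for hourly vital signs for at least 4 hours

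*Combined protocol and SAP*

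**What the plan says.** Each patient receives two infusions: "1 IV infusion on Day 1 and 1 IV infusion on Day 8" (section 3.1).

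For a patient who has gone home before Day 8, section 3.1 says that "they will return for an outpatient visit to receive the second IV infusion and remain at the site for an approximate 2-hour observation period". The synopsis and section 5.5.3 repeat the instruction.

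Section 8.9 sets the vital-sign schedule around dosing: before the infusion, every 15 minutes during it, at its end, and then "hourly post-infusion, for a minimum of 4 hours after each infusion within a window of" 5 minutes either side. It covers both infusions and draws no distinction between inpatients and outpatients.

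In the visible text, nothing says which instruction governs the outpatient Day 8 visit.

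**The concern.** Sites have two different lengths of post-infusion monitoring for the same visit. A site that plans the visit from the 2-hour sentence, which appears three times, has no prompt there to keep the patient longer. A site that plans from section 8.9 will keep the patient for 4 hours. With about 10 sites in two countries, practice could easily differ.

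The readings at stake have a use. The safety endpoints in section 8.1 include "Change from screening (baseline) in clinical symptoms and abnormal vital signs". Appendix C describes infusion-related reactions in terms of blood pressure, heart rate, respiratory rate and oxygen saturation, and the section 8.9 vital signs cover the first three.

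The DMC reviews each sentinel cohort 7 days after its last dose, so Day 8 data feed that review. After Cohort 2, "the DMC will convene and review all available safety data to determine if the study can proceed to the next dose level". These decisions rest on few patients: 2 on F-652 in each sentinel cohort and 9 on F-652 across Cohorts 1 and 2. The patients whose readings may be cut short are also those with no ward monitoring once they leave.

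**Working it through.** The plan has no figure of its own to reproduce here, and the sample size is "not based on statistical power calculation". The check compares two timing rules and counts readings.

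**Inputs**
- Outpatient stay after the Day 8 infusion: about 2 hours (synopsis, 3.1, 5.5.3).
- Post-infusion vital signs: hourly for at least 4 hours, window 5 minutes either side (8.9).
- Other infusion-related readings: one before, one every 15 minutes during, one at the end (8.9).
- F-652 patients: 2 in Cohort 1, 7 in Cohort 2, 2 in Cohort 3 (3.1).
- Infusion duration: not visible; 30 to 120 minutes is assumed.

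**Step 1: hourly readings.** They fall due at 1, 2, 3 and 4 hours. A stay of about 2 hours reaches the first two. The earliest allowed times for the others are 3 h − 5 min = 2 h 55 min and 4 h − 5 min = 3 h 55 min, so the window does not close the gap. Missed: 2 of 4 = 50%. This takes the 2 hours as starting when the infusion ends, which is the natural reading. If they started with the infusion, the shortfall would be larger.

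**Step 2: all readings around one infusion.** For an infusion of D minutes, the total is 1 (before) + (D/15 − 1) (during) + 1 (end) + 4 (hourly) = D/15 + 5.

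| Assumed D | Total readings | Share missed |
|---|---|---|
| 30 min | 7 | 2/7 = 28.6% |
| 60 min | 9 | 2/9 = 22.2% |
| 120 min | 13 | 2/13 = 15.4% |

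**Step 3: what the DMC would lack on active drug.** Count only the 3- and 4-hour readings after the second dose, two per patient.
- One sentinel cohort: 2 × 2 = 4 readings. One F-652 outpatient released at about 2 hours removes 2/4 = 50%.
- Cohorts 1 and 2 together: (2 + 7) × 2 = 18 readings. One such patient removes 2/18 = 11.1%.

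The number of such patients is not given, so these are losses per affected patient and not expected losses.

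**The case against.** The strongest objection is that the deciding text may be hidden. Redacted lines directly follow the 2-hour sentence in section 5.5.3. Section 6 says "Study procedures will follow the Schedule of Procedures", and that schedule (Appendix A) is not shown. Either could hold an outpatient rule. This stands as a reason to check first. It does not remove the conflict: section 8.9 and the outpatient sentence in the synopsis and section 3.1 are fully visible without an exception. Sections 8.7, 8.10 and 8.11 do attach conditions for patients still in hospital, and 8.9 does not. Even if an exception exists elsewhere, 8.9 would need a cross-reference.

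Second, the two rules do not strictly contradict each other. The 2 hours is approximate and is never called a maximum, so a 4-hour stay satisfies both. That also stands, but it leaves the choice to each site. A site could equally read the outpatient sentence as the specific rule and 8.9 as the general one.

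Third, the consequence is limited. Patients are in hospital for the first dose, so it is unaffected. The visible safety analysis is descriptive and names no 3- or 4-hour timepoint. The triggers in section 4.3.2 are clinical events, and adverse events are collected to Day 60. Section 3.2.1, on the criteria for DMC review, is not shown, so how far the DMC relies on these readings is unknown. All of this stands and sets the scope. It does not justify leaving sites with two rules for post-infusion safety monitoring.

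**Conclusion.** The concern holds on the visible text. The outpatient instruction and section 8.9 give different monitoring times after the same infusion, and following the shorter one costs half of the hourly post-infusion readings for that dose.

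The conclusion assumes that the 2 hours run from the end of the infusion and that no exception sits in the text not shown. The 50% sentinel and 11% Cohorts 1 and 2 figures also assume one F-652 outpatient released at about 2 hours.

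The problem is confined to vital signs after the second dose in patients already discharged. Readings up to about 2 hours, the ECG at about 30 minutes after the infusion, adverse-event collection and the ITT efficacy analysis are untouched. It should be corrected because it bears on outpatient safety monitoring and on whether the DMC sees comparable data in very small groups.

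**What to change.** First look in the unredacted section 5.5.3 and in Appendix A for an outpatient Day 8 exception. If there is one, refer to it in section 8.9.

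If there is none, the preferred change is to set the outpatient stay in the synopsis, section 3.1 and section 5.5.3 to at least 4 hours after the end of the infusion, matching 8.9. This costs wording in three places and about 2 more hours on site per outpatient second dose. It keeps all four hourly readings.

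If the clinical team judges 2 hours sufficient, add one sentence to section 8.9 limiting hourly vital signs after an outpatient Day 8 infusion to 1 and 2 hours. That gives sites one rule but gives up two hourly readings per outpatient second dose, so it restores consistency without improving the monitoring.
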